4.11.3 Deaths, Serious Adverse Events, and Other Significant Adverse Events

Reporting of Deaths, Serious Adverse Events and other significant Adverse Events is described in the above section 4.11.2.

4.11.4 Clinical Laboratory Evaluation

All clinical laboratory test results will be presented and summarized using the International System of Units (SI units; Système International d'Unités). The original lab test units will be converted to SI according to *Young, D.S and Huth, E.J; 1998; SI Units for Clinical Measurement; American College of Physicians; Philadelphia and Burtis, C.A, Ashwood, E.R and Bruns, D.E; 2008; Fundamentals of Clinical Chemistry; Saunders Elsevier; Missouri* [Laboratory test converted to SI will be stored in SDTM LB domain as LBSTRESU and LBSTRESC]. Additionally, clinical laboratory test results will be converted in Conventional Units, and store in SDTM SUPPLB domain.

All clinical laboratory test results will be graded per NCI CTCAE v4.03 if applicable, as well as high (higher than the normal range), normal (in the normal range) and low (lower than normal range).

Descriptive statistics (n, mean, standard deviation, median, and range) of the lab parameters and changes from baseline will be presented by regimen and dose group for biochemistry, hematology, and coagulation. Such descriptive statistics will be presented at Baseline and at End of Study, as well, Worst Result post Baseline (i.e. Maximum and Minimum post Baseline including results from unscheduled assessments) will be presented as well.

Shift in biochemistry, hematology, and coagulation result CTCAE grading from baseline will be tabulated at the end of treatment, as well as from baseline to the maximal grade during the study (maximal grade will also include results from unscheduled and repeated assessments).

PAREXEL International
Statistical Analysis Plan Template for Early Phase Studies

Symphegen A/S
Sym013-01

All clinical laboratory test results will be listed in the original, SI, and Conventional units, for biochemistry, hematology, coagulation, and urinalysis.

Individual patient biochemistry, hematology, and coagulation parameters during the trial can be presented graphically using longitudinal spaghetti plots. Specific lab parameters to be plotted will be decided by Symphegen from clinical meaning perspective after examination of corresponding listings.

Biochemistry, hematology, and coagulation parameters will be presented using box plots by visits and tumor type.

Results from the pregnancy tests will be listed.

4.11.5 Electrocardiogram

ECG parameter data will be listed by part dose group, time point, and patient.

Normal, abnormal, or abnormal clinically significant ECG will be summarized by regimen, dose at Baseline, EOT and Worst Post Baseline; as well, a shift table from baseline to EOT and Worst Post Baseline will be summarized by cohort. Number and percentage of patients with end of treatment and maximum postdose QTcF values of ≤ 450 , > 450 ms and ≤ 480 , > 480 ms and ≤ 500 , and > 500 ms, and maximal change from baseline values of ≤ 30 , $> 30 \leq 60$ ms, and > 60 ms will be summarized by part and dose group (highest QTcF Prolongations measurement will also include results from unscheduled assessments). Above categories of QTcF are based on ICH E14[2].

4.11.6 Echocardiogram (ECHO) or Multi-Gated (MUGA) Scan

ECHO/MUGA data will be listed.

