3.2.4.2 Other Anticipated Clinical Findings

Dermatological toxicities, such as acneiform rash, dry skin, fissures, and paronychia are common AEs associated with EGFR inhibitors, in particular EGFR targeting antibodies, such as cetuximab and panitumumab (16). Other common side effects often associated with anti-EGFR mAbs are electrolyte disturbances, in particular hypomagnesemia, and IRRs.

Cardiotoxicity in the form of left ventricular dysfunction has been observed in association with HER2 inhibition, in particular with trastuzumab treatment (16). The risk increases in combination with anthracyclines.

Diarrhea is a common side effect of many cancer treatments, including chemotherapeutic agents and targeted therapeutics (16,17). EGFR-targeted TKIs are associated with high frequencies of clinically important diarrhea. Diarrhea is also common with several multi-agent HER2-directed regimens used in the treatment of HER2-positive breast cancer. HER3 targeting antibodies do not seem to induce much diarrhea or other severe AEs on their own, but increased frequencies of diarrhea have been observed in combination with EGFR targeted therapeutics such as erlotinib and cetuximab (18,19). Prophylaxis with agents that decrease intestinal motility, such as loperamide, appears to effectively reduce the incidence and severity of diarrhea caused by HER family targeting (17,20).

Based on nonclinical results, the AE most likely to be seen with Pan-HER is diarrhea.

Confidential Page 29 of 156

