9.1.2 Events Not to be Considered as Adverse Events

A pre-existing condition (i.e., a disorder that is present before the AE recording period starts and is noted on the medical history/physical examination form) should not be recorded as an AE unless the condition worsens, or episodes increase in frequency during the AE recording period. Refer to **Section 9.2.1**

PD will not be captured as an AE unless the nature of the PD is different than expected (i.e., signs/symptoms that are not typical of PD).

Note: PD may be reported as an AE in the case of patient death, with death being the outcome of the event.

An abnormal laboratory value or an abnormality in physiological testing (such as ECGs) per se need not be reported as an AE unless one of the following applies:

- The Investigator considers the abnormality clinically significant
- The event meets the definition of an SAE
- The event requires an intervention
- The event results in an action taken with Pan-HER (dose-reduction and/or withdrawal)

Diagnostic and therapeutic non-invasive and invasive procedures, such as surgery, should not be recorded as AEs. A medical condition for which an unscheduled procedure was performed, should however be recorded if it meets the definition of an AE. For example, an acute appendicitis should be recorded as the AE and not the appendectomy.

Confidential Page 86 of 156

Procedures to support the treatment regimens, such as insertion of central venous catheters etc. should not be recorded as AEs, unless the procedures result in complications.

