9.5 Dose-Limiting Toxicities (Part 1 Only)

9.5.1 Definition of Dose-Limiting Toxicities

A DLT is defined as any of the following toxicities that occur during the DLT-observation period, if considered related (causality rating of possibly, probably, or related) to Pan-HER:

- 1. Grade 3 non-hematologic toxicity regardless of duration, with the exception of:
 - a. Grade 3 nausea, vomiting, diarrhea, or fatigue lasting ≤2 days with best supportive care
 - b. Grade 3 asymptomatic electrolyte abnormality that is not considered clinically significant by the Investigator and that is controlled with medical therapy
- 2. Grade 4 non-hematologic toxicity, with the exception of:
 - a. Grade 4 asymptomatic electrolyte abnormalities that is not considered clinically significant by the Investigator and that is controlled with medical therapy
- 3. Neutropenia that is:
 - a. Grade 3-4 febrile neutropenia
 - b. Grade 4 and sustained (i.e., ANC $< 0.5 \times 10^9 / L [500 / mm^3]$, duration > 5 days)
- 4. Thrombocytopenia that is
 - a. Grade 3 with clinically significant hemorrhage

Confidential Page 92 of 156

- b. Grade 4 (platelets $<25 \times 10^9/L [25,000/mm^3]$)
- 5. AST/ALT elevation >3×ULN with bilirubin elevation >2×ULN without evidence of cholestasis that cannot be explained by factors not related to Pan-HER
- 6. Evidence of cardiac toxicity as defined by either:
 - a. ≥16% absolute decrease in LVEF from baseline, or
 - b. LVEF below the institutional lower limit of normal and ≥10% absolute decrease in LVEF from baseline
- 7. Inability to complete Cycle 1 at the assigned dose due to \geq Grade 3 toxicity
- 8. Treatment delays >2 weeks from the scheduled next dose due to \ge Grade 3 toxicity

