All listings will display the same number of decimals as in the source data. All raw data will be reported exactly as provided.

Quantitative derived variables (e.g. Duration of Response, Time to Progression, Actual Treatment duration) will be shown with 1 decimal place (d.p.) precision.

PAREXEL International
Statistical Analysis Plan Template for Early Phase Studies

Symphegen A/S
Sym013-01

The data for the patients who consented but for any reason did not receive any dose of study drug (including screening failures) will be also listed but with a label of '*' and a footnote to flag these.

Efficacy, Exposure and PK/PD Data Listing will be based on Full Analysis Set.

Tables and Descriptive Statistics

Unless specified otherwise all tables and statistics will be presented using the FAS.

Evaluation of DLT will not be based on FAS but on DLT Analysis Set.

Unless specified otherwise summary tables and figures will be presented by dose regimen (Q1W or Q2W), dose group, and visit (where applicable); also, overall summaries will be shown for the two-dosage regimen and for all patients pooled together. In general, summary tables will be structured in three parts: first part will summarize overall results obtained in the two dose regimens Q1W, Q2W and in all patients pooled together; second part will display all dose groups within the dosage regimen Q1W; third part will display all dose groups within the dosage regimen Q2W.

In general, for variables showing multiple possible categories, these will be displayed with following the within variable logic criteria, for example: ECOG categories will be displayed from 0 and going to grow; where such a logic criterium does not exist (example: gender, ethnicity, SOC, PT), categories will be displayed by descending frequencies based on the overall all patients pooled together. In the end, the order used to show categories within variables should be the same in the three parts of each table.

Unless otherwise stated, continuous data will be summarized using descriptive statistics including: number of non-missing observations (n), arithmetic mean, standard deviation (SD), median, minimum, and maximum.

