Listing 14.3.2.1 Serious Adverse Events - Key Patient Information (Full Analysis Set) *

Listing 14.3.2.2 Adverse Events with Outcome of Death - Key Patient Information Full Analysis Set *

Listing 14.3.2.3 Adverse Events Leading to Permanent Discontinuation of Investigational Product - Key Patient Information Full Analysis Set *

Listing 14.3.2.4 Adverse Events Leading to Dose Reduction - Key Patient Information Full Analysis Set *

Listing 14.3.2.5 Adverse Events Leading to Infusion Interruption or Stop - Key Patient Information Full Analysis Set *

PAREXEL International
Statistical Analysis Plan Template for Early Phase Studies

Symphegen A/S

Sym013-01

Listing 14.3.2.6 Listing of Death- Key Patient Information (Full Analysis Set) *

Listing 14.3.4.1 Abnormal Hematology Values *

Listing 14.3.4.2 Abnormal Chemistry and Coagulation Values *

Listing 14.3.4.3 Abnormal Urinalysis Values *

Table 14.3.5.1 Clinical Laboratory Hematology-Summary of Observed Values and Change from Baseline (Full Analysis Set) *

Table 14.3.5.2 Clinical Laboratory Chemistry-Summary of Observed Values and Change from Baseline (Full Analysis Set) *

Table 14.3.5.3 Clinical Laboratory Coagulation-Summary of Observed Values and Change from Baseline (Full Analysis Set) *

Table 14.3.5.4 Clinical Laboratory Hematology -Summary of CTCAE Grade Shift from Baseline to Maximal Grade (Full Analysis Set) *

Table 14.3.5.5 Clinical Laboratory Chemistry –Summary of CTCAE Grade Shift from Baseline to Maximal Grade (Full Analysis Set) *

Table 14.3.5.6 Clinical Laboratory Coagulation –Summary of CTCAE Grade Shift from Baseline to Maximal Grade (Full Analysis Set) *

Table 14.3.6.1 Vital Signs and Weight Observed Values and Change from Baseline (Full Analysis Set) *

Table 14.3.6.2 ECG Clinical Assessment (Full Analysis Set) *

Table 14.3.6.3 ECG Shift from Baseline (Full Analysis Set) *

Table 14.3.6.4 ECG– QTcF Prolongations Summary (Full Analysis Set) *

Table 14.3.6.5 Physical Examination Clinical Assessment (Full Analysis Set)

Table 14.3.6.6 Physical Examination Shift from Baseline (Full Analysis Set) *

PAREXEL International
Statistical Analysis Plan Template for Early Phase Studies

Symphegen A/S

Sym013-01

Table 14.3.6.7 ECOG-PS (Full Analysis Set)

Table 14.3.6.8 ECOG-PS Shift from Baseline (Full Analysis Set) *

Figure 14.2.1 Skin Biopsy: scatter plot of EGFR receptors down modulation at C1D8 and C1D15 versus Baseline (Full Analysis Set) *

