Listing 16.2.8.3 Clinical Laboratory Urinalysis Results (All Consented Patients) *

Listing 16.2.8.4 Pregnancy Test (All Consented Patients) *

Listing 16.2.9.1 Vital Signs – Observed and Change from Baseline Values (All Consented Patients) *

Listing 16.2.9.2 Electrocardiogram (All Consented Patients) *

Listing 16.2.9.3 ECHO/MUGA(ECHO) (All Consented Patients) *

Listing 16.2.9.4 Physical Examination (All Consented Patients)

Listing 16.2.9.5 ECOG-PS (All Consented Patients) *

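### LVEF is only listed, so an asymptomatic fall past the protocol's cardiac-toxicity limits reaches a summary table only if it is reported as a DLT or as an AE

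*SAP*

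**What the plan says.** Protocol 3.2.4.2 states the class risk: "Cardiotoxicity in the form of left ventricular dysfunction has been observed in association with HER2 inhibition". Protocol 7.2.2.2 repeats it for anti-HER2 drugs and names dilated cardiomyopathy.

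Protocol 9.5.1 item 6, repeated in SAP 3.2.4.1, gives two limits, neither of which requires symptoms. Item 6a is a 16% or greater "absolute decrease in LVEF from baseline, or" item 6b, which is an LVEF below the institutional lower limit of normal with an absolute fall of at least 10%. Protocol 7.1.4.3 uses the same limits as a dose-reduction criterion.

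ECHO or MUGA is scheduled at screening and at EOT, with other scans only as clinically indicated (protocol 8.2.8, SAP 3.2.4.5). SAP 3.2.4 names ECHO/MUGA among the safety endpoints.

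The whole analysis text, SAP 4.11.6, is "ECHO/MUGA data will be listed". The only matching entry in SAP section 6 is "Listing 16.2.9.3 ECHO/MUGA(ECHO) (All Consented Patients"), which is marked for the abbreviated report.

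**The concern.** Cardiac toxicity in this protocol is a change-from-baseline quantity, and no planned output is specified to contain that change. Assessments less specific to the HER2 risk get more. The vital signs listing is titled "Listing 16.2.9.1 Vital Signs – Observed and Change from Baseline Values (All Consented Patients"), and ECG has threshold counts in "Table 14.3.6.4 ECG– QTcF Prolongations Summary (Full Analysis Set").

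The AE tables are not a reliable substitute. Under protocol 9.1.2 an "abnormality in physiological testing (such as ECGs) per se need not be reported as an AE unless one of the following applies": clinical significance in the investigator's view, seriousness, need for intervention, or action on the study drug.

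At stake is the primary objective, safety and tolerability. The summary tables could show no cardiac signal while the raw listing holds falls that meet the protocol's own limits.

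**Working it through.** The plan states no figure on this point, so there is nothing to reproduce. The check counts outputs, traces the routes to a table, and applies the limits to examples.

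**1. Outputs in SAP section 6**

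| Assessment | Summary tables | Change, shift or threshold count? |
|---|---|---|
| ECHO/MUGA | 0 | none |
| ECG | 3 (14.3.6.2 to 14.3.6.4) | shift and QTcF thresholds |
| Vital signs | 1 (14.3.6.1) | change from baseline |
| Physical examination | 2 (14.3.6.5, 14.3.6.6) | shift |
| ECOG | 2 (14.3.6.7, 14.3.6.8) | shift |

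Shortening the report does not explain the gap: the ECG and vital signs tables all keep their asterisk. Nor does the general rule in SAP 4.2, "Unless otherwise stated, continuous data will be summarized using descriptive statistics including", close it, because 4.11.6 specifies a listing and section 6 has no ECHO/MUGA table.

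**2. Routes by which a fall meeting item 6 reaches a table**

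- *DLT.* A fall rated related and found in the Cycle 1 window enters Table 14.2.4.8. This needs a scan in that window, and none is scheduled on treatment. An EOT scan falls there mainly when a patient stops early. The table draws on a Yes/No CRF field (SAP 3.2.4.1), with no derived check against measured LVEF.
- *Dose action.* A related fall found on treatment meets the 7.1.4.3 criterion. A resulting dose action makes it an AE under 9.1.2, so it enters the TEAE tables. This also needs an on-treatment scan.
- *Investigator report.* A fall judged clinically significant, serious or in need of intervention is an AE. This stays open at EOT, because AEs are recorded up to the 1-month follow-up visit (9.2.1).

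The EOT visit follows the decision to discontinue (protocol 5.3.4). For an asymptomatic fall first seen there, the dose-action route is closed and the DLT route usually is too. Investigator reporting is mostly what remains.

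**3. The limits applied to examples**

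Let fall = baseline − EOT, in LVEF percentage points. The lower limit of normal is assumed to lie between 50 and 55, because the protocol uses the institution's own value.

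- 70 to 54: fall = 16, so 6a is met.
- 60 to 48: fall = 12, and 48 is below any limit from 50 to 55, so 6b is met.
- 60 to 51: fall = 9, so neither is met.

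The first two, found at EOT without symptoms and not reported as a DLT or AE, would be seen only as raw values in Listing 16.2.9.3.

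**4. Scale of a count (illustrative)**

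The exact two-sided 95% upper limit for 0 events in n patients is 1 − 0.025^(1/n).

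- n = 19 (entered by Amendment 6, protocol 3.2.4.1): 1 − 0.025^(1/19) = 0.176, or 17.6%.
- n = 34 (planned for Part 1, protocol 5.5): 1 − 0.025^(1/34) = 0.103, or 10.3%.

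Only patients with both a baseline and a post-baseline scan would count. The documents give neither that number nor the final enrolment.

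**The case against.** A reader might infer that such falls can enter no safety table at all. The documents do not support that. The limits are themselves a DLT criterion and a dose-reduction criterion, neither needs symptoms, and DLTs and AEs are tabulated. Protocol 7.2.2.2 also counts LVEF decrease among clinically relevant cardiac AEs, although it does so for scans prompted by symptoms. It is therefore not safe to assume that an investigator would leave a fall past the limit unreported.

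A reader might also infer that the report could give no rate. That too goes too far. Listing 16.2.9.3 is kept for the abbreviated report and is ordered by regimen, dose group, patient and visit (SAP 4.2). With usually two scheduled values per patient, the change is one subtraction and a count can be made by hand.

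Nor has the SAP dropped a commitment. Protocol 10.4.3 does not name LVEF as a safety endpoint and promises no LVEF summary.

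Finally, the trial stopped in Part 1. The cohorts at Amendment 6 held 1, 1, 4, 3, 7 and 3 patients, so statistics by dose group will be thin and individual values are readable.

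All of this stands, and it limits the point. It does not remove it: for the asymptomatic fall first seen at EOT, entry to a table still depends mostly on individual reporting, and nothing planned checks the measured values against the protocol's limits.

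**Conclusion.** The point holds in a limited form, as an analysis choice worth improving. LVEF has 0 summary tables and one listing, with no planned change from baseline and no count against item 6. An asymptomatic fall meeting item 6, most likely first seen at EOT, enters no summary table unless it is reported as a DLT or the investigator reports it as an AE.

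This rests on three assumptions. LVEF is taken to be recorded as a number. Listing 16.2.9.3 is taken to show raw values only, because its title names no change while the vital signs listing does. Asymptomatic patients are taken to have no unscheduled on-treatment scan. How many patients, if any, are affected cannot be told from the documents, and the 17.6% for 0/19 is for scale only.

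**What to change.** In SAP 4.11.6, derive the absolute LVEF change from baseline for every post-baseline ECHO/MUGA, including unscheduled scans. SAP 4.2 already has the baseline and worst-value rules.

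Add one table to section 6, marked for the abbreviated report, by regimen, by dose group and overall, with:

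- baseline, EOT and worst post-baseline LVEF, and the change;
- n/N meeting item 6a, where N is the number of patients with baseline and post-baseline values;
- n/N meeting item 6b where the institutional lower limit is recorded, stating for how many it is. The documents do not show that it is collected.

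Add change and criterion-met columns to Listing 16.2.9.3.

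Flag changes measured across modalities (ECHO against MUGA), which protocol 8.2.8 does not rule out. Leave them out of the descriptive change statistics only. Keep them in the criterion counts with the flag, because item 6 makes no distinction by modality.

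The cost is one table shell and a few derived variables, with small numbers per dose group. No new assessment is needed, and no dose or clinical rule changes.

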4.11.7 Vital Signs and Body Measurements

Data for vital signs (body weight, blood pressure, heart rate, temperature) will be listed by part, dose group, patient, at Baseline and EOT.

PAREXEL International
Statistical Analysis Plan Template for Early Phase Studies

Symphogen A/S
Sym013-01

Descriptive summary statistics (for observed values and changes from baseline) for vital sign parameters (blood pressure and heart rate) will be provided for Baseline, EOT and Worst Result post Baseline (i.e. Maximum and Minimum post Baseline including results from unscheduled assessments) by regimen and dose group.

4.11.8 Physical Examination

All abnormal findings from the physical exam will be listed.

A shift table from baseline to EOT and worst from baseline of normal and abnormal findings in physical examination by regimen and cohort will be produced.

4.11.9 Eastern Cooperative of Oncology Group (ECOG) Performance Status (PS)

ECOG performance status will be listed and summarized by shift table from baseline to EOT and worst from baseline.

4.11.10 Safety Monitoring (Independent Data Monitoring Committee [IDMC], Data Monitoring Committee [DMC], Data and Safety Monitoring Board [DSMB])

A safety monitoring committee (SMC) was established and included Investigator(s), Medical Monitor(s) and Sponsor's medical representatives. The SMC reviewed clinical and laboratory safety data regularly throughout the trial and will select the RP2D and regimen to be used in Part 2 based on safety data, as well as available PK and target engagement results. Additionally, the annual Development Safety Update Report (DSUR) was submitted by Symphogen or designee to all appropriate HAs and central IRBs/ECs as per ICH Guidelines. Submission of the DSUR to local IRBs/ECs has been handled as per local regulations and/or requests.

4.12 Other Analyses

No other analyses.

4.13 Determination of Sample Size

No formal testing of hypotheses has been planned in this study. Therefore, no formal sample size calculations were performed.

PAREXEL International
Statistical Analysis Plan Template for Early Phase Studies

Symphegen A/S
Sym013-01

4.14 Changes in the Conduct of the Study or Planned Analysis

The trial has been stopped during Part 1, no patient is enrolled in Part 2. Part 2 of the trial did not take place.

- Objectives for Part 2 are omitted. Per protocol, the concentration of total Pan-HER (the sum of the serum concentration for all six mAbs) was planned to be used for the PK analysis. However, in an exploratory analysis, the PK of the six mAbs was shown not to be similar, and hence using the sum of concentrations is not justified. Hence, the PK of each mAb is reported;
- Overall Survival was planned as one of the Protocol Endpoints, this analysis will not be performed: patients in this study are not followed up to death so that OS would result in a truncated biased estimate;
- Time to documented PD, death, patient withdrawal or end of trial participation, whichever comes first was initially planned in the Protocol Endpoints. Actually, based on FDA guideline as of December 2018 [3], TTP is mentioned as a possible endpoint for oncological studies, '*TTP is defined as the time from randomization until objective tumor progression; TTP does not include deaths.*' TTP will be used as an endpoint in this study instead of the planned time to documented PD, death, patient withdrawal or end of trial participation.
- Duration of SD was initially planned in the Protocol Endpoints, anyway this endpoint is overlapping with TTP being derived in a very similar way; thus, this endpoint will not be part of the data analysis.
- DCR analysis was not included as part of study endpoints in the Protocol, such analysis has been added in this SAP.

Given the early interruption of the trial, Symphegen decided to proceed with an abbreviated Clinical Study Report; from list of Tables, Figures and Listings reported in below section 6, only those flagged with asterisk (*) will be produced for the abbreviated CSR.

PAREXEL International
Statistical Analysis Plan Template for Early Phase Studies

Symphogen A/S

Sym013-01

